8.4 Handling of Plasma Concentrations that are Below the Lower Limit of Quantification

Plasma concentrations that are below the limit of quantification (BLQ) will be handled as follows for descriptive statistics:

- Pre-dose concentrations that are BLQ will be treated as zero.
- Post-dose concentrations that are BLQ will be treated as missing.
- Values below the limit of quantification (BLQ) that are set to 0 in the source dataset will be treated as 0 in the calculation of summary statistics.
- Missing values will be excluded from the calculation of means, and n will reflect the actual number of values used in the calculation.
- Arithmetic mean or median values that are BLQ will be presented as 0.
- If any pre-dose BLQ results (treated as 0) are in a series of summarized data, geometric mean and coefficient of variation (CV) % of geometric mean will be reported as not calculated (NC).

8.5 Multi-Center Studies and Pooling of Centers

Although this is a multi-center study, all subjects from all centers will be pooled together for analysis. Treatment-by-center interaction will not be assessed.

8.6 Multiple Comparisons/Multiplicity

Hypotheses tested will be adjusted to control the familywise error rate in the strong sense at $\alpha = 0.050$, 2-sided. An adjustment of 0.0001 will be made to account for the unblinded data summaries reviewed by the DMC. The hypotheses will therefore be tested at $\alpha = 0.0499$.

The statistical comparisons for the primary efficacy endpoint and the secondary endpoints, all at Week 12, will be carried out in sequential order. The primary endpoint, comparing izokibep to placebo, will be tested first, with significance concluded if $p < 0.0499$. Testing of secondary endpoints will only be carried out if all prior tests, including the test of the primary endpoint, first show significance with $p < 0.0499$. If all prior tests are significant, testing will proceed in the following order:

- The first secondary endpoint: proportion of subjects achieving HiSCR90 at Week 12.
- The second secondary endpoint: proportion of subjects achieving HiSCR100 at Week 12.
- The third secondary endpoint: proportion of subjects achieving HiSCR50 at Week 12.
- The fourth secondary endpoint: change in DLQI from baseline to Week 12.
- The fifth secondary endpoint: achieving AN count of 0, 1, or 2 at Week 12 among subjects with baseline Hurley Stage II.
- The sixth secondary endpoint: proportion of subjects who achieve a reduction in pain NRS of at least 3 points from baseline to Week 12, among subjects with a pain NRS score of at least 4 at baseline.
- The seventh secondary endpoint: proportion of subjects who experience flares through Week 12.

If a null hypothesis is not rejected, p-values for subsequent hypotheses in the sequence will be reported as nominal and will not be used to assess objectives or make determinations of efficacy.

At the time of the primary analysis of Week 12 data, some data was available for subjects at Week 16, but not all. A cutoff date was chosen and subjects randomized before that cutoff date were included in summaries and analyses of Week 16 data; subjects randomized after that cutoff date were excluded from summaries and analyses of Week 16 data. When all subjects have completed or discontinued the terminated study at Week 32, a final analysis will be reported, which will include Week 16 data. Since Week 16 data will not be used for any alpha-preserving analyses, there will be no multiplicity adjustment for analyzing Week 16 data twice.

8.7 Interim Analyses and Data Monitoring Committees

An independent Data Monitoring Committee (IDMC) is established to monitor data on an ongoing basis to ensure the continuing safety of the subjects enrolled in this study.

The DMC consists of at least 1 medical expert with the relevant therapeutic area and at least 1 statistician. The DMC has a minimum of 3 members, 1 of whom serves as the Chair. The DMC responsibilities, authorities, and procedures will be documented in the DMC charter. The committee will meet as needed to review significant safety findings. After each review, the DMC will make recommendations regarding the continuation of the study based on safety. The DMC will not be empowered to recommend stopping this study or changing the sample size due to a demonstration of positive efficacy.

Data may be summarized for a DMC at regular intervals during the study to ensure safety of study subjects. The type I error rate for hypothesis tests at the end of the study will be decreased by 0.0001 to account for each interim summary of unblinded data.

After all subjects have had an opportunity to complete the Week 12 visit (complete the visit, or complete a subsequent visit, or permanently discontinue the study before Week 12), the primary endpoint analyses will be conducted. Site staff, and all sponsor staff who interact with site staff, will remain blinded to individual subject treatment assignment until the final subject has completed the final visit and the database lock has occurred.

At various points after the primary analysis, analyses of data collected after Week 12 will be reported for regulatory submission purposes or other reasons. These analyses will be documented. No adjustment to the type I error rate will be applied due to these summaries, because the inferential statistics will already have been determined.

8.8 Examination of Subgroups

No subgroup analyses will be performed for the purposes of the abbreviated CSR.

9. STATISTICAL ANALYSIS

9.1 Subject Disposition and Analysis Sets

Study disposition will be summarized for each treatment group and overall for the All Screened Set. The following information will be included:

- The number of subjects Screened
- The number and percentage of subjects for the following categories:
 - Randomized

- Treated
- Not treated
- Completed Week 12 Assessment
- Completed Study at Week 12
- Discontinued Study Before Week 12
- Reasons for Study Discontinuation before Week 12
- Completed Week 16 Assessment
- Completed Study at Week 16 (Period 1)
- Discontinued Study before Week 16 (within Period 1)
- Reasons for Study Discontinuation Prior to Completing Week 16 (Period 1)
- Completed the Week 52 Assessment
- Completed Study at Week 52 (Period 2)
- Discontinued Study before Week 52 (within Period 2)
- Reasons Study Discontinuation Prior to Completing Week 52 (within Period 2)
- Discontinued from the study prior to Week 16 (Period 1)
- Discontinued Study before Week 52
- Reasons for Study Discontinuation Prior to Completing Week 52
- Completed Study
- Discontinued Study
- Reasons for discontinuing study
- Number and percentage of subjects included in, and excluded from, each analysis set together

The denominator for the calculations above will be the number of randomized subjects in each group, except for the proportion of subjects randomized. For the proportion of subjects randomized, the denominator will be the number of subjects screened.

Treatment disposition will be summarized for each treatment group and overall for the FAS. The following information will also be included:

- The number and percentage of subjects for the following categories:
 - Completed treatment through Week 11
 - Discontinued from treatment before Week 11
 - Reasons for treatment discontinuation prior to the Week 11
 - Completed treatment through Week 15 (Period 1)
 - Discontinued from treatment prior to Week 15 (within Period 1)
 - Reasons for Treatment Discontinuation before Week 15 (within Period 1)
 - Completed treatment through Week 51 (Period 2)
 - Discontinued from treatment before Week 51 (within Period 2)
 - Reasons for Treatment Discontinuation before Week 51 (within Period 2)
 - Discontinued from treatment any time before Week 51
 - Reasons for Treatment Discontinuation any time before Week 51
 - Discontinuing treatment within the following time categories:
 - Day 1
 - Day 2 - Day 14 (within 2 weeks)
 - Day 15 - Day 28 (>2 - 4 weeks)
 - Day 29 - Day 56 (>4 - 8 weeks)

- Day 57 - Day 98 (>8 - 12 weeks)
- Day 99 - Day 112 (>12 - 16 weeks)
- Day 113 – Day 140 (>16 - 20 weeks)
- Day 141 – Day 168 (>20 – 24 weeks)
- Day 169 – Day 224 (>24 – 32 weeks)
- Day 225 – Day 364 (>32 – 52 weeks)
- > Day 364 (> 52 weeks)

9.2 Protocol Deviations

Protocol deviations will not be summarized or listed for the abbreviated CSR. The data will be available in the SDTM datasets.

9.3 Demographics and Baseline Characteristics

Demographic parameters and other baseline characteristics will be summarized by treatment group and overall for the FAS.

Descriptive statistics (n, mean, SD, median, minimum, and maximum) will be summarized for:

- Age (years) at Screening
- Height (cm)
- Weight (kg)
- Body Mass Index (kg/m²)
- Body Temperature (C)
- Respiratory Rate (breaths per minute)
- SBP (mmHg)
- DBP (mmHg)
- Heart Rate (bpm)
- Time since diagnosis with HS (years)
- AN Count
- Abscess Count
- Draining Fistula Count
- Non-Draining Fistula Count
- Total Fistula Count
- Inflammatory Nodule Count
- Non-inflammatory Nodule Count
- HADS Total Score
- HADS-Anxiety
- HADS-Depression
- PGA
- DLQI
- EQ-5D (Domain Scores [Mobility, Self-Care, Pain/Discomfort, Usual Activities, and Anxiety/Depression], Index Score, Visual Analog Scale (VAS) Score)
- SF -12 (Mental Component Score and Physical Component Score)
- NRS Pain – At its worst
- NRS Pain – On average

- IHS4
- HiSQOL

The number and percentage of subjects in each category will be summarized by treatment group and overall for the FAS:

- Age groups: <65 years vs. ≥65 years
- Sex
- Race
- Ethnicity
- Hurley Stage (II, III) (Using the 'worst case' value collected on the baseline Lesion Counts eCRF page)
- Childbearing potential (Yes, No)
- Alcohol Use (Never, Current, Former)
- Nicotine Use (Never, Current, Former)
- C-SSRS – Lifetime Ideation
- C-SSRS – Past 6 Months Ideation
- Location of lesions

Medical History will be summarized by treatment group and overall for the FAS. The number and percentage of subjects with at least 1 medical history event will be presented. The number and percentage of subjects and in each system organ class (SOC) and preferred term (PT) will be summarized. Subjects will be counted once within each SOC and PT. The summary will be sorted using the internationally agreed order for SOC and using descending order of overall numerical counts for PT. Where terms tie, these will be sorted alphabetically.

9.4 Prior and Concomitant Medications

Prior and concomitant medications will be summarized separately for the FAS by treatment group and overall. The number and percentage of subjects with at least 1 prior/concomitant medication will be presented. The number and percentage of subjects with at least 1 prior/concomitant medication within each Anatomical Group (ATC Level 1), Therapeutic Subgroup (ATC Level 2), and preferred term will be presented. The summary will be sorted using numerical counts by descending order of Anatomical Group, then descending order of Therapeutic Subgroup, then descending order of preferred term in the total column. Where groups or terms tie these will be sorted alphabetically.

Concomitant medications will be summarized for Period 1, and, separately, for Period 2.

9.5 Analysis of Primary Efficacy Endpoint

The primary efficacy variable is defined as HiSCR75 at Week 12.

The statistical null and alternative hypotheses to be used to assess the primary objective are:

$$H_0: \pi_{ABY} - \pi_{PBO} = 0$$

$$H_A: \pi_{ABY} - \pi_{PBO} \neq 0$$

where π_{ABY} and π_{PBO} are the proportion of subjects achieving HiSCR75 at Week 12 among subjects randomly assigned to receive izokibep and placebo, respectively.

The treatment policy strategy approach for the estimand will be used in general, so subjects will be included using observed data at Week 12 regardless of treatment compliance, use of rescue medications or procedures except as noted below, or any other protocol deviations.

Subjects who receive antibiotic therapy that could affect HS will be included in the primary analysis by imputing as non-responders (non-response imputation or NRI) at subsequent timepoints. A list of all oral antibiotic therapy that results in such imputation will be finalized after review of all oral antibiotic therapy received by any subject and before unblinding of the study, and will include tetracycline, clindamycin, and possibly other products. Similarly, subjects with missing HiSCR75 assessments at Week 12 due to discontinuing treatment due to an AE or lack of efficacy will also be imputed as NRI. These subjects will be identified by meeting any of the following criteria:

- Subject has adverse event with action taken = “Drug Withdrawn” and corresponding AE start date is before study day 84 and last dose of study drug is taken before study day 84 or
- Subject has last dose of study drug taken before study day 84 and reason for discontinuation of treatment is any of the following:
 - Adverse event
 - Death
 - Lack of efficacy
 - Disease progression

Other subjects with missing data will have efficacy data imputed using multiple imputation, as follows:

Multiple imputation will be implemented to replace missing endpoint data using multiple draws from a posterior predictive distribution estimated from the placebo group only. First, a monotone missingness pattern will be enforced using Markov Chain Monte Carlo (MCMC). The MCMC process will use predictor variables of:

- baseline abscess count (continuous)
- baseline inflammatory nodule count (continuous)
- baseline draining fistula count (continuous)
- age (continuous)
- baseline BMI (continuous)

for nonmonotone missingness at Week 2 (missing at Week 2 but available at a later timepoint). MCMC predictors in the regression model for missing values after Week 2 will include the predictor variables listed above, plus:

- counts of abscess (continuous)
- inflammatory nodule (continuous)
- and draining fistula (continuous)

collected at prior scheduled assessments. After monotone missingness is enforced, missing HiSCR75 at Week 2, 4, 8, 12, and 16 will be imputed, assuming monotone missingness pattern. Any missing HiSCR75 will be imputed by first imputing components of the AN count (abscess and inflammatory nodules) and draining fistula count, then assigning HiSCR75 status from the imputed values. Predictors in the regression model for missing values at Week 2 will be:

- baseline Hurley stage (II/III) ('worst case' value selected from the Lesion Count eCRF page at baseline)
- baseline abscess count (continuous)
- baseline inflammatory nodule count (continuous)
- baseline draining fistula count (continuous)
- sex (male/female)
- race (white/non-white)
- age (continuous)
- BMI (continuous)
- Prior Biologic/Janus Kinase (JAK) Inhibitor Use for HS (yes/no).
- baseline smoking/tobacco status (current, former, never)
- highest categorization of location of baseline HS abscesses (difficult to treat, easier to treat)
 - A subject can have HS abscesses in multiple locations around their body and will indicate each location at baseline. The locations are categorized based on how difficult they are to treat (in bullets below). The subject will be assigned to a category based on the location of their most difficult to treat abscess at baseline.
 - Difficult to treat: left/right axilla, left/right sub/inframammary region, left/right buttock, left/right inguinocrural fold, perianal, perineal, genitalia, gluteal cleft, labia majora, abdominal cavity, arm, flank, thigh, mammary, mons pubis, thigh, vulva, scrotum, sternum, stomach fold, suprapubic region, chest, sacrum, inframammary, labia majora, sternal area, face, jaw area, and breast
 - Easier to treat: all remaining locations
- highest categorization of location of baseline HS draining fistulas (difficult to treat, easier to treat, per logic described above)
- highest categorization of location of baseline HS inflammatory nodules (difficult to treat, easier to treat, per logic described above)

Predictors in the regression model for missing values after Week 2 will be all these variables, plus:

- counts of abscess (continuous)
- inflammatory nodule (continuous)
- and draining fistula (continuous)

at prior scheduled assessments.

Missing HiSCR75 values in both the placebo group and the izokibep group will be imputed using observed data from the placebo group only.

Data will be processed sequentially by repeatedly calling SAS® PROC MI to impute missing outcomes at Week 4, 8, 12, and 16. A total of 100 imputations will be imputed to form the complete data set with a pre-specified seed (891523) to ensure reproducibility. These multiple imputed data sets are then analyzed by using the same method for the primary analysis for complete data. The final inference on treatment difference is conducted from the multiple datasets using Rubin's combining rules. Imputed values without rounding will be used at each imputation step.

Example SAS code for the PROC MI procedure described above:

```
/*Imputation to monotone missing pattern*/  
  
proc mi data = data seed=891523 n impute = 100 out = t2  
    min = .....  
    0 0 0 0 0;  
    var age bmibl bl_abscnt bl_infnctn bl_dfistcnt week_2 week_4 week_8 week_12  
        week_16;  
    mcmc chain = multiple impute = monotone;  
    EM MAXITER=1000000;  
    run;  
/*Complete imputation*/  
  
proc mi data = data seed=891523 out = out n impute = 1 minmaxiter=600  
    min = .....  
    .....;  
    by _imputation_;  
    class trt01p stratum1 sex race stratum2 locdiff_ab locdiff_df locdiff_in smkstat;  
    var bl_abscnt bl_infnctn bl_dfistcnt locdiff_ab locdiff_df locdiff_in smkstat sex race  
        stratum1 stratum2 age bmibl week_2 week_4 week_8 week_12 week_16;  
    monotone reg (week_2 = bl_abscnt bl_infnctn bl_dfistcnt locdiff_ab locdiff_df locdiff_in  
        smkstat sex race age bmibl stratum1 stratum2);  
    monotone reg (week_4 = bl_abscnt bl_infnctn bl_dfistcnt locdiff_ab locdiff_df locdiff_in  
        smkstat sex race age bmibl stratum1 stratum2 week_2);  
    monotone reg (week_8 = bl_abscnt bl_infnctn bl_dfistcnt locdiff_ab locdiff_df locdiff_in  
        smkstat sex race age bmibl stratum1 stratum2 week_2 week_4);  
    monotone reg (week_12 = bl_abscnt bl_infnctn bl_dfistcnt locdiff_ab locdiff_df  
        locdiff_in smkstat stratum1 stratum2 sex race age bmibl week_2 week_4  
        week_8);  
    monotone reg (week_16 = bl_abscnt bl_infnctn bl_dfistcnt locdiff_ab locdiff_df  
        locdiff_in smkstat stratum1 stratum2 sex race age bmibl week_2 week_4  
        week_8 week_12);  
    mnar model(week_2 week_4 week_8 week_12 week_16 / modelobs= (trt01p='Placebo QW'));  
    run;
```

locdiff_ab = location difficulty of abscesses; locdiff_df = location difficulty of draining fistulas; locdiff_in = location difficulty of inflammatory nodules; trt = treatment group; smkstat = smoking status; strat = stratum; bl_abscnt = baseline abscess count; bl_infnctn = baseline inflammatory nodule count; bl_dfistcnt = baseline draining fistula count

Other imputation, fully conditional specification method may be implemented if the multiple imputation model does not converge. If imputation is not possible due to sparseness of data for certain predictor variables, that predictor variable will be collapsed into a single category, in essence removing that predictor from the predictor model. In the case that baseline predictors need to be removed from the model, the location difficulty of inflammatory nodules variable will be removed first, followed by location difficulty of abscesses, location difficulty of draining fistulas, smoking status, sex, race, age, BMI, baseline abscess count, baseline inflammatory nodule count, and baseline draining fistula count. The number of iterations may be increased, if the imputed values are outside the allowable specifications.

If negative values result from the multiple imputation procedure, then these will be set to 0.

Results from all runs will be combined using Rubin's rule (Rubin, 1987), resulting in a single point estimate, a single CI, and a single p-value. If the imputed datasets do not contain sufficient variability to combine them together, then the first imputed dataset will be selected for analysis and statistical summaries will be run based on that data.

The number of subjects imputed with NRI as well as the number of subjects imputed with multiple imputation will be tabulated with reasons for imputation at Week 12.

A stratified test of response rates will be used for the primary analysis. Within each of the 4 strata used for randomization, the response rate for each treatment group and corresponding standard error will be calculated. The difference in response rates (risk difference) will be calculated for each stratum. The common risk difference among the 4 strata and associated standard error will be estimated by combining the observed risk differences using Cochran-Mantel-Haenszel weighting. The estimated risk difference divided by the standard error will be used as the test statistic and a p-value calculated assuming that the test statistic follows a standard normal distribution under the null hypothesis. Analyses at earlier timepoints when data to calculate the HiSCR75 are collected will also be presented using the same methodology. P-values from earlier timepoints and Week 16 will be presented for descriptive purposes, not part of the alpha-preserving multiple testing strategy.

Sample SAS code with stratification factors of comparing each dosing regimen of izokibep to the combined placebo group is given as following:

```
ods output commonpdiff = ;
proc freq data= ;
  tables stratum * treatment * response / cmh commonriskdiff (test=mh cl=mh);
  weight count / zeros;
run;
```

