6.2.2 Visit and Timepoint Windows

In general, data will be analyzed using the nominal study visits as defined in the SoA in the protocol and reported on the eCRF.

If a subject discontinues the study early, the subject will have an early termination visit which includes efficacy and safety assessments. If the early termination visit occurs in a timeframe that corresponds to a scheduled efficacy or safety assessment (week 2, 4, 8, 12, 16, 20, 24, 32, or 52), and if the subject does not have an actual visit at or after the corresponding scheduled efficacy or safety assessment, the day ranges below will be used to map the early termination visit to a scheduled efficacy assessment for use in all efficacy summaries at that timepoint.

In addition, unscheduled visit results will not be included in analyses, unless the unscheduled visit corresponds to a nominal visit for which the result is missing or if the unscheduled visit is selected as baseline. If the nominal visit result is missing, then the unscheduled visit result will also be mapped according to the ranges in Table 1 and Table 2 below for efficacy and safety assessments, respectively. If multiple unscheduled visits fall into 1 analysis window, then the one closest to the scheduled day will be used for analysis. If the 2 unscheduled visits are equidistant from the scheduled day, the later assessment will be used.

Table 1: Visit Windowing for Efficacy Assessments

Nominal Visit	Scheduled Day	Analysis Window (Relative Days)
Day 1/Week 0 (Baseline)	1	[1, 1]
Week 2	14	[2, 21]
Week 4	28	[22, 42]
Week 8	56	[43, 70]
Week 12	84	[71, 98]
Week 16	112	[99, 140]
Week 24	168	[141, 196]
Week 32	224	[197, 294]
Week 52	364	[295, later]

Table 2: Visit Windowing for Safety Assessments:

Nominal Visit	Scheduled Day	Analysis Window (Relative Days)
Day 1/Week 0 (Baseline)	1	[1, 1]
Week 2	14	[2, 21]
Week 4	28	[22, 42]
Week 8	56	[43, 70]
Week 12	84	[71, 98]
Week 16	112	[99, 126]
Week 20	140	[127, 154]
Week 24	168	[155, 196]
Week 32	224	[197, 294]
Week 52	364	[295, later]

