6.7 Primary Efficacy Endpoint

The primary endpoint of the study is HiSCR75, the proportion of subjects achieving at least a 75% reduction from baseline in the total AN count, with no increase from baseline in abscess or draining fistula count, at Week 12.

The proportion of subjects achieving HiSCR75 will be defined as meeting all 3 criteria below at a specific assessment:

- $[(\text{AN count at baseline} - \text{AN count at current visit}) / \text{AN count at baseline}] \times 100\% \geq 75\%$
- Abscess count at baseline \geq abscess count at the current visit

- Draining fistula count at baseline \geq draining fistula count at the current visit

where AN count is abscess count + inflammatory nodule count, and abscess count, inflammatory nodule count and fistula count are summed across all regions and are inclusive of all abscesses, inflammatory nodules and fistula that have previously undergone localized surgical or medical intervention and are no longer present.

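### SAP 9.5 derives HiSCR from unrounded, normal-model lesion counts, so an imputed subject with a zero baseline abscess or draining fistula count fails on any positive fraction; the effect on the primary test is small

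*SAP*

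**What the plan says.** SAP 6.7 defines HiSCR75 as at least a 75% fall in AN count "with no increase from baseline in abscess or draining fistula count, at Week 12". For both components the baseline count must be at least the visit count. Eligibility (Protocol 5.1) sets a floor only on the AN total, at 5, so a baseline of 0 abscesses or 0 draining fistulas is allowed.

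Some missing Week 12 data never reach multiple imputation. Subjects given antibiotics that could affect HS, and those with missing data after stopping treatment for an AE or lack of efficacy, count as non-responders. SAP 6.2.2 also fills gaps from other visits: "If the nominal visit result is missing, then the unscheduled visit result will also be mapped according to the ranges", and early termination visits are mapped in a similar way.

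For the remaining subjects SAP 9.5 imputes the three component counts, "then assigning HiSCR75 status from the imputed values". Two steps do this:

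- An MCMC step ("mcmc chain = multiple impute = monotone") fills intermittent gaps.
- A sequential linear regression step fills the rest.

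On the form of the values, the SAP says "Imputed values without rounding will be used at each imputation step" and "If negative values result from the multiple imputation procedure, then these will be set to 0". It has no rule for positive fractions and no rounding before status is assigned. HiSCR50, 90 and 100 follow the same approach (SAP 9.6).

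**The concern.** A lesion count cannot be 0.2, but a normal model produces such values. When the baseline component is 0, the no-increase rule demands exactly 0 at Week 12, so 0.2 is scored as worsening. Take a baseline of 0 abscesses, 5 nodules and 0 fistulas, with imputed Week 12 values of 0.2, 0 and 0. The AN reduction is (5 - 0.2)/5 = 96%, yet the subject is a non-responder.

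In the regression step only draws at or below 0 can pass. In the example MCMC call the `min=` list has five dots followed by five zeros, and the ten variables end with the five week variables, so the zeros fall on the weeks. A continuous draw bounded below at 0 is essentially always positive, so a zero-baseline component filled there is essentially certain to fail. That step decides Week 12 only for subjects with no Week 12 value, mapped visits included, who are seen again at Week 16.

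At stake is a bias in the primary endpoint whose size depends on how many subjects are imputed in each arm. Protocol 2.2.3.2 reports high drop-out among responders on 160 mg QW in the preceding HS study. SAP 9.5.1 drops the sensitivity analyses that might have shown the effect.

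**Working it through.** **Plan's own figure.** SAP 4.4 gives about 95% power for 15% against 35%, 125 per arm, two-sided 0.05, unstratified.

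- Null SE = sqrt(2 x 0.25 x 0.75/125) = 0.0548.
- Alternative SE = sqrt(0.15 x 0.85/125 + 0.35 x 0.65/125) = 0.0533, or 5.3 points.
- (0.20 - 1.96 x 0.0548)/0.0533 = 1.74, so power is 95.9%. The figure reproduces.

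**One zero-baseline component, regression step.** Let the predictive draw have mean mu and SD s (both assumed). The chance of passing is Phi(-mu/s) unrounded and Phi((0.5 - mu)/s) rounded to the nearest integer.

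- mu = 0.25, s = 1: Phi(-0.25) = 40% against Phi(0.25) = 60%.
- Two such components, taken as independent: 0.40^2 = 16% against 0.60^2 = 36%.
- Over mu from 0 to 1 and s from 0.5 to 2: 2-50% against 16-84%.

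**Simulation, placebo arm.** The documents give no count distributions, so these are assumed:

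- Poisson counts with a subject effect at Weeks 2, 4, 8, 12 and 16; baseline AN at least 5, fistulas at most 20.
- Zero baseline abscess in 17-42% of subjects, zero baseline fistula in 27-50%; six settings.
- True Week 12 HiSCR75 fixed at 15% and 35%.
- Imputation by placebo-fitted linear regression on baseline counts and the component's own Week 2, 4 and 8 values, negatives set to 0.

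| Placebo, imputed at Week 12 | Unrounded | Rounded | Predictive mean matching | True |
|---|---|---|---|---|
| No increase, zero baseline | 21-26% | 31-38% | 51-65% | 56-69% |
| HiSCR75 | 7.1-9.0% | 10.6-11.2% | 11.8-12.4% | 15% |
| HiSCR100 | 3.1-3.8% | 5.1-6.1% | 1.6-2.1% | 2.4-2.9% |

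Further runs with other assumed distributions gave HiSCR75 of 7.2-8.1%, 9.9-10.3% and 12.5-13.0% for the three methods.

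Most affected subjects would be non-responders anyway. With a zero baseline, true HiSCR75 is 15-16% on placebo and 34-35% on izokibep, so about 85% and 65% do not respond.

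**Risk difference.** Shift = (izokibep missing rate x change in its imputed response) - (placebo missing rate x change in its imputed response), with data missing completely at random.

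| Missing, placebo/izokibep | Unrounded minus matching | Unrounded minus rounded |
|---|---|---|
| 10%/10% | -0.42 to -0.54 point | -0.09 to -0.19 point |
| 10%/20% | -1.16 to -1.57 | -0.36 to -0.75 |
| 20%/10% | -0.04 to -0.15 | not tabulated |

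The further runs gave -0.28 to -0.35, -1.00 to -1.23 and about +0.1 to +0.2 against matching, so the sign at 20%/10% is not settled.

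Against the SE of 5.3 points, the largest shift is 1.57/5.3 = 0.30 SE. The part due to rounding is at most 0.75/5.3 = 0.14 SE.

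**At trial size** (125 per arm, about 112 placebo donors, Rubin's rules, unstratified test):

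- 10%/10%: shift -0.31 to -0.36; power 93.5-94.9% unrounded against 94.4-95.3% with matching.
- 10%/20%: shift -1.05 to -1.28; power 86.6-89.9% against 90.1-92.3%.

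**Arms in the first call.** SAP 9.5 and Protocol 9.3.2 call for estimation from placebo data. The example MCMC call has no treatment variable, BY statement or subset; the placebo restriction appears only in the second call. In the simulation, pooling the arms moved the risk difference by -0.006 to +0.042 point.

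**The case against.** The strongest reply is that the no-rounding sentence speaks of imputation steps, so it governs values carried from one step to the next and leaves the HiSCR derivation open. The wording does allow that. But the derivation is stated to work from the imputed values, and no rule turns a fraction into a count. A programmer following the SAP would compare 0.2 with 0.

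Second, rounding is a minor part of the shift. This stands: most of the gap to predictive mean matching is misfit of a normal model to counts. Nor is matching the truth. It leaves HiSCR75 2.6 to 3.2 points below 15% in the main simulation, and it misses HiSCR100 by about as much as unrounded values do, in the other direction.

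Third, the direction depends on the model. If one imputed rate q applied to both arms, 10% missing in each would give 0.9 x (35 - 15) = 18.0 points whatever q is. But the SAP conditions on each subject's own earlier counts. Izokibep dropouts with good earlier counts therefore have more responses to lose, which produces the small negative shift at equal missingness.

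Fourth, the code is labelled an example and is schematic. That stands, and it limits the point about arms: a reader might infer that izokibep data would inform the imputation, but the text plainly says otherwise.

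Finally, the SAP will tabulate how many subjects are imputed by each method at Week 12, with reasons, so the exposure can be judged.

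**Conclusion.** The rule as written gives a wrong result for a definable group: subjects with a zero baseline abscess or draining fistula count whose Week 12 value for that component is imputed. It is a minor point. Compared with predictive mean matching, the HiSCR75 risk difference moves by about -0.3 to -0.5 point at 10%/10% missing (placebo/izokibep), by -1.0 to -1.6 at 10%/20%, and by close to zero with either sign at 20%/10%. Rounding itself accounts for about 0.1-0.2 point in the first case and 0.4-0.75 in the second. All sizes rest on assumed count distributions and missing rates.

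Two stronger readings are not supported. A reader might infer that dropouts filled in the regression step always fail. That would need a lower bound of 0 on the weeks in the second call ("proc mi data = data seed=891523 out = out n impute = 1 minmaxiter=600"). Its `min=` line shows only ten dots for 18 variables, so its bounds cannot be read. The remark "The number of iterations may be increased, if the imputed values are outside the allowable specifications" hints that bounds may exist, but the rule setting negatives to 0 would be needless if both calls were bounded there. A reader might also infer that the primary conclusion is unsafe. A shift of at most about 0.3 SE would rarely change it, and in the scenarios with a clear sign it works against izokibep.

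**What to change.** Impute the three components by predictive mean matching from placebo donors, so that imputed counts are whole numbers, and then derive HiSCR50, 75, 90 and 100. SAP 8.6 describes the Week 12 analysis in the past tense, so keep that result as run and report this version as a documented supplementary analysis.

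The cost is some code, a short SAP addition and one extra run in an abbreviated report. The method needs enough placebo donors (about 112 sufficed in the trial-size check) and puts imputed HiSCR100 somewhat low. Rounding after negatives are set to 0 is only a partial fallback: it recovers part of the HiSCR75 shortfall and inflates imputed HiSCR100.

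Separately, reconcile the placebo-only text with the example MCMC call. This is not a one-line edit, because that call fills gaps for subjects of both arms without a treatment term. Either specify how placebo-only estimation is done there, or state that this step pools the arms. The numerical effect is negligible.
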